**TEMPLATE: RESEARCH PROTOCOL**

NUMBER	ACTIVE DATE	PAGE
HRP-503	02-04-2020	19 of 35

	Clinician Monitoring and Respiratory System Monitoring typically conducted by various surgical team members assigned for the patient's surgical procedure.
	18.3 How will the safety information will be collected?
	Safety information will be collected by the patient's surgical team in the charting conducted both pre and post operatively to coincide with UCMC's current standards of care for surgical procedures.
	18.4 The frequency or periodicity of review of cumulative data.
	The review will follow the duration of the surgical procedure and standard six-week follow-up provided by the patients care team.
	18.5 Who will review the data?
	Data will be reviewed by the surgical team members.
	18.6 The statistical tests for analyzing the safety data to determine whether harm is occurring.
Statistical testing will follow the outlined analysis for this current study as stated in the protocol.	
18.7 Any conditions that trigger an immediate suspension of research.	
The standard procedure is to not use a model, and thus we believe that looking at the model before the procedure is genuinely minimal risk. The surgeon will have already performed the review of the imaging (that forms the basis of the physical model), and therefore there is no risk of increased OR time for any patient. As we stated in the second to last paragraph of Page 3 in the initial submission, we are looking at potentially less time in the OR, as there will not be more time spent in the OR for any patient. This is looking to redefine the current standards of care minimizing the OR time already expected under the normal standards of care. No conditions would trigger immediate suspension as current standards of care will be utilized throughout surgery.	
19.1 Describe the provisions to protect participants' privacy and to minimize the intrusiveness of the study questions or procedures.	
Subject confidentiality will be protected to the extent permitted by law. Electronic databases with subject identifier will also be user-access protected. Subject identifiers will not be used, since medical record numbers will be replaced by de-identified patient ID numbers. The research data will be periodically reviewed by study team members to ensure that patient information and privacy is not at risk of being compromised. Patient privacy during evaluations and procedures will be maintained via standard-of-care HIPAA protocols.	

**19.0 PARTICIPANT  
PRIVACY**

20.0 COMPENSATION FOR RESEARCH RELATED INJURY	20.1 For more than minimal risk research, describe the available compensation in the event of research-related injury.
	Not Applicable- even though the research is labeled as more than minimal risk, the same standard surgical procedure will be carried out regardless of the use of the 3D model. Any complications that arise unexpectedly will be covered under UCMC surgical consent the patient signs before surgery that is routine for all surgical procedures conducted in the hospital.
	20.2 Provide a copy of contract language relevant to compensation for research-related injury.
21.0 ECONOMIC BURDEN TO SUBJECTS	21.1 Describe any costs that subjects may be responsible for because of participation in the research.
	There is no additional cost for the subjects for participation in the study

22.0 CONSENT	
22.1 Obtaining consent – Check applicable and complete the corresponding section(s). Please note, sections 23-28 each apply under different circumstances. Please complete the correct sections as checked in this section (e.g. if you do not request a waiver of documentation of consent, do not complete section 24)
	
		The research team will obtain written consent from all subjects. (Complete section 23) ( HRP-502M TEMPLATE Medical Informed Consent or HRP-502S TEMPLATE SBER Informed Consent or HRP-502V TEMPLATE VA Informed Consent )
		The research team will obtain consent from all subjects but is requesting a waiver of documentation (signature) of consent. (Complete sections 23 and 24) ( HRP-502I TEMPLATE Information Sheet )
		The research team is requesting a waiver or alteration of the consent process. (Complete section 25)
		The research team is requesting Exception from Informed Consent for emergency research. (Please complete the EFIC supplement document and upload under number 3 on the local site documents page in RAP)
		The research team will enroll Non-English-speaking subjects and obtain consent (written or otherwise). (Complete sections 23 and 26)
		The research team will enroll subjects who are not yet adults (infants, children, teenagers) and will obtain written consent from the subject's parent(s) or guardian(s). (Complete sections 22 and 27) ( Parent Permission Template )
		The research team will enroll adult subjects unable to provide consent (cognitively impaired individuals) and will obtain written consent from the subject's Legally Authorized Representative. (Complete sections 23 and 28)

23.0 CONSENT PROCESS	
23.1 Where will the consent process take place?
 
For patients:
 
A research team member will go over the consent form with potential subjects in a private area and will answer any questions subject may have. Subject will be given a copy of the consent and time as needed to consider enrolling in the study. A phone number will be given in case the subject has additional questions. All subjects are to receive copies of their signed consent form. The date the subject signs the consent form is to be recorded on CRF.
 
For surgeons:
 
The research coordinator will go over the consent form with the surgical team members in a private area and will answer any questions subject may have. The surgeons will be given a copy of the consent and time as needed to consider enrolling in the study. A phone number will be given in case the subject has additional questions. All subjects are to receive copies of their signed consent form. The date the subject signs the consent form is to be recorded on CRF.

	
23.2 Is there a waiting period available between informing the prospective subject and obtaining the consent?
 
There will be a minimal waiting period, (< 60 minutes) between informing prospective patients of interest in study involvement and obtaining consent.

	
23.3 Describe:
 
 
• The role of the individuals listed in the application as being involved in the consent process.
 
• The time that will be devoted to the consent discussion.
 
• Steps that will be taken to ensure the subjects' understanding.
 
• Steps that will be taken to minimize the possibility of coercion or undue influence.
 

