**4.1 Detail the investigators' experience as it pertains to the study.**

**4.0 INVESTIGATOR EXPERIENCE**

[name] has been a member of the UC Surgery faculty since 2008. He is currently associate professor of surgery and is serving as the chief of OMS at UC Medical Center and Cincinnati Children's Hospital. [name] obtained his dental degree from Bangalore University, India, and trained in Oral and Maxillofacial Surgery at Emory University's College of Medicine in Atlanta, Georgia. Upon completion of residency, [name] pursued further fellowship training in Oral & Maxillofacial Surgery focusing on orthognathic surgery at Dalhousie University, Halifax, Canada. He currently serves on the Committee of Education and Training (CET) of the AAOMS and is the chair of the special committee on Emerging leaders in OMS. He is also a consultant to the AAOMS Committee on Anesthesia (CAN) on Simulation in Anesthesia. [name] was in the first class of single degree oral and maxillofacial surgeons that were recognized as Fellows of the American College of Surgeons.

[name] is Vice Chair of Operations & Quality at the University of Cincinnati Department of Radiology, and he is the clinical lead for the 3D printing section at UCH. He is the past-Chair of the American College of Radiology Appropriateness Criteria, and the Founding Chair of the Radiological Society of North America 3D Printing Special Interest Group. He also is currently the Editor-in-Chief of the journal 3D Printing in Medicine. [name] obtained his medical

	
degree through the physician scientist program at Harvard -MIT (Medicine and Medical Engineering), and he completed his residency in Diagnostic Radiology at the Brigham and Women's Hospital and Harvard Medical School, Boston, MA.

5.0 STUDY ENDPOINTS	
	
5.1 Describe any primary and secondary study endpoints.
 
Outcome 1: Noninferiority of the clinical outcome (defined by OMS on the post-op, follow up exam approx. 6 weeks out) Based on physical exam
 
Outcome 2:
 
 
Total time in the OR
 
Time in the OR considered critical part of the procedure by the OMS Staff
 
 
Outcome 3
 
 
Subjective outcome to surgeon Likert scale
 
 
5.2 Describe any primary and secondary safety endpoints.
 
Not Applicable.

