	
6.1 Thoroughly describe the study design.
 
We plan to conduct a randomized controlled trial on trauma patients brought to either UCMC or UC HH OMS for treatment of isolated mandibular fractures. This study plans to elucidate whether the utilization of 3D models during operations where effective in minimizing both OR time and operational costs. Subjects will be identified based off the initial physical assessments made by surgical specialists from OMS, Plastic Surgery, and otolaryngology. Once the subjects are identified the research coordinator will conduct a screening of the patient to ensure they meet the inclusion/ exclusion criteria for the study and then randomize the patient into either normal standard of care for surgical repair of the fractured mandible or normal standard of care for surgical repair of the fractured mandible aided by a 3D printed model of the patient's jaw. Any chart reviewing will be conducted from existing electronic medical records maintained by UC Health EPIC and OMS Vision. All the following data would be based on the patient's condition at the time of surgery.

	
Following completion of the procedure, for the surgeons who received aide via the 3D model they will be asked to answer a brief Likert Scale survey outlining their thoughts how effectively or ineffectively the model assisted them. In addition to this information, if they feel the model increased efficiency saving time, they will be asked to state how much time they felt was saved. This time differential will be compared to current CPT codes for OR time to understand how much in operational costs were saved by utilizing the models.

6.0 PROCEDURES INVOLVED	

6.2 Detail the procedures being performed, specifically the interaction or intervention with human subjects and/or their identifiable information. Please be clear and concise and provide information relevant to the current study. For
	

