**TEMPLATE: RESEARCH PROTOCOL**

NUMBER	ACTIVE DATE	PAGE
HRP-503	02-04-2020	11 of 35

10.0 INCLUSION AND EXCLUSION CRITERIA & VULNERABLE POPULATIONS
	
10.1 Describe how subjects will be screened for eligibility.
 
The screening of potential participants will be performed by the providers of University of Cincinnati Medical Center's Department of Oral and Maxillofacial Surgery clinic located at Holmes Hospital (UCMC OMS HH clinic), or surgical providers from plastic surgery and otolaryngology located in UCMC including resident physicians, attending physicians, research staff, and clinic staff. Surgical team members from the division of plastic and otolaryngology will be consented and recruited to participate in this study by providing their feedback post operatively. The diagnosis and treatment planning will strictly be made by a resident or attending surgeon. However, an elected research coordinator will complete a standardized eligibility form on REDCap based on the study's inclusion/exclusion criteria to finalize participant selection
	
	
10.2 Describe/list the inclusion/exclusion criteria for the study.
 
Inclusion Criteria:
 
Patient ≥ 18 years of age
 
Patients who have received either a cone beam or conventional CT
 
Admitted through UCHMC emergency department
 
All isolated mandible fractures referred to UCH OMS
 
Surgical team members from the division of plastic and otolaryngology
 
Exclusion Criteria:
 
Patient < 18 years of age
 
Patients who have neither cone beam nor conventional CT
 
Patients requiring a repeat procedure
 
Unexpected exposure of hardware
	
	
10.3 Indicate specifically whether you will include each of the following vulnerable populations. Check all that apply. (You may not include members of the below populations as subjects in your research unless you indicate this in your inclusion criteria and are approved by the IRB to include them in your research) The member checklists are for reference only to ensure you provide appropriate safeguards and justification. The checklists do not need to be completed.
	

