
17.0 DATA MANAGEMENT AND CONFIDENTIALITY
	
17.1 Describe the data analysis plan, including any statistical procedures or power analyses.
 
We are going to use the Likert questions to develop a numerical scoring system and report that data as “raw” Likert scores. Likert questions and conversion of specialists’ responses to Anatomic Model Utility Points (AMUPs). Responses of “strongly disagree”, “disagree”, and “neutral” were assigned 0 AMUP points. Responses to preprocedural confidence are assigned negative points, to effectively subtract the impact of the anatomic model post- versus pre-procedure. The maximum AMUP for each patient was 500.

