18.0 PROVISIONS TO MONITOR THE DATA TO ENSURE THE SAFETY OF SUBJECTS	
18.1 For more than minimal risk research, describe the plan to periodically evaluate the data collected regarding both harms and benefits to determine whether the subjects remain safe.
 
The participants will be undergoing surgical repair at UCMC for a mandible fracture. The participants participation in the study only lasts for the duration of the procedure. The evaluation of the data will be assessed following the completion of the procedure by the surgeon consented for participation in answering the Likert Scale questions. Routine surgical monitoring associated with current standards of care will be conducted by the surgical staff in the procedure room as assigned on the patients care team.
 
18.2 What data are reviewed, including safety data, untoward events, and efficacy data?

---	---

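### Section 18.6 refers the harm analysis to a stated analysis that holds only a one-arm surgeon rating, and the listed study data contain no harm variable, so no between-arm comparison of harm is specified

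*Protocol*

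**What the plan says.** Section 18.6 asks for the statistical tests used to decide whether harm is occurring. The full answer is "Statistical testing will follow the outlined analysis for this current study as stated in the protocol". No variable, comparison or test is named there.

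Section 17.1, the data analysis plan, opens with "We are going to use the Likert questions to develop a numerical scoring system" and goes on to convert the answers to Anatomic Model Utility Points (AMUPs). It says nothing else about analysis. Section 6.1 says who is surveyed: "for the surgeons who received aide via the 3D model they will be asked to answer a brief Likert Scale survey". Section 23.3 agrees that a surgeon answers only when assigned to use the model.

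Under the prompt "Describe any primary and secondary safety endpoints", section 5.2 answers that this is not applicable. Section 17.5 lists three kinds of data: procedural time, cost differential and the surgeons' Likert answers.

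Other sections point the other way. Section 18.3 has the surgical team chart safety information before and after the operation. Section 18.4 extends the review to the standard six-week follow-up. Outcome 1 in section 5.1 is noninferiority of the clinical outcome, judged by physical examination at about six weeks. Section 18.1, however, says "The participants participation in the study only lasts for the duration of the procedure".

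Two further statements bear on harm. The exclusion criteria in 10.2 include patients who need a repeat procedure and "Unexpected exposure of hardware". Section 18.7, in explaining why nothing would trigger suspension, states that "there will not be more time spent in the OR for any patient".

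**The concern.** A cross-reference is harmless if its target does the job. Here the target is a rating of how useful the model was, collected in one arm. It has no control-arm counterpart and does not measure what happened to the patient.

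Section 1.2 defines the intervention as 3D printing with a pre-bent plate, so an implanted component is prepared differently in the two arms. Section 18.7 says the study looks to redefine the current standard of care. If the protocol is followed as written, a shorter time in the operating room could be reported without reoperation, hardware exposure or infection by arm. The document neither shows nor rules out an effect of the pre-bent plate on such events, which is the reason to count them.

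The statements on follow-up and exclusions could make this worse. If participation ends with the procedure, the six-week information falls outside the study. If the two exclusions in 10.2 were applied after surgery, they would remove the events that signal harm.

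**Working it through.** **1. Tracing the cross-reference.** The protocol states no figure to reproduce: 50 procedures per arm are given in 11.1 without alpha, power, event rates or a noninferiority margin. The check is therefore a reading of the sections against each other.

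| Question | Where | What is found |
|---|---|---|
| Which analysis does 18.6 use? | 18.6 | The one stated in the protocol |
| What is stated? | 17.1 | Raw Likert scores and AMUPs |
| Any other calculation? | 6.1 | Surgeon-estimated time saved, converted to cost |
| In which patients? | 6.1, 23.3 | 3D-model arm only, for both |
| Any safety endpoint? | 5.2 | Not applicable |
| Any harm field in the study data? | 17.5 | None |
| Is safety information charted? | 18.3 | Yes, as standard care, so in both arms |
| For how long? | 18.4 against 18.1 | To six weeks, against end of procedure |
| Any between-arm clinical outcome? | 5.1, Outcome 1 | Yes, but no field in 17.5 and no analysis in 17.1 |

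The chain from 18.6 ends at a one-arm utility score. The chain from 18.3 and 18.4 ends in the patient's chart and does not reach the study data list. Outcome 1 is named but reaches neither the data list nor the analysis plan.

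**2. What a comparison at 50 per arm could deliver.** All event rates below are assumptions, since the protocol gives none.

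*Zero events in one arm.* The exact upper limit solves (1 − p)^50 = α.
- Two-sided 95%: 1 − 0.025^(1/50) = 0.071, or 7.1%.
- One-sided 95%: 1 − 0.05^(1/50) = 0.058, or 5.8%.

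*Power of Fisher's exact test, 50 per arm, two-sided 0.05.* This is the sum of the two binomial probabilities over all pairs of counts with p ≤ 0.05.

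| Assumed control rate | Assumed 3D rate | Power |
|---|---|---|
| 5% | 10% | 0.06 |
| 10% | 20% | 0.19 |
| 10% | 25% | 0.41 |
| 10% | 30% | 0.64 |

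*Precision.* With a 10% rate in both arms, the approximate 95% half-width of the risk difference is 1.96 × √(2 × 0.10 × 0.90 / 50) = 1.96 × 0.060 = 0.118, or about 12 percentage points.

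The comparison can be made, but it can only describe. A doubling of an uncommon complication would usually be missed by a test.

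**The case against.** The strongest counter-argument is Outcome 1. A noninferiority comparison of the six-week clinical outcome asks whether the 3D arm does worse, and chart data exist for both arms. A reader might infer from 18.6 and 5.2 that harm cannot be compared at all, or that the trial has no ability to show a difference. The document does not support that. What it supports is narrower: no such comparison is specified, and the listed data do not supply one.

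Second, 17.1 gives no between-arm test for operating-room time either, and event definitions and table layouts are commonly left to a SAP, which is not shown here. That is true of missing detail. It does not rescue 18.6, which positively fixes the harm analysis as the one in the protocol, nor the answer in 5.2, which conflicts with 18.3 and 18.4.

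Third, a reader might take the two items in 10.2 as harms being removed from the results. They stand among eligibility criteria, and the coordinator completes the eligibility form at screening, so they can describe baseline conditions such as an earlier failed repair. The word for unexpected exposure sits awkwardly with that reading. The wording is ambiguous and calls for clarification, not a finding that harms are discarded.

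Fourth, a reader might infer from 18.7 that nothing is monitored. Sections 18.1 to 18.5 describe monitoring during surgery, charting and review to six weeks. What stands against 18.7 is that it states as fact what 1.2 sets out to test.

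Finally, low power limits what the fix can deliver. This stands, and it shapes the remedy.

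**Conclusion.** The point holds in this form: the analysis to which 18.6 assigns harm carries no information on harm and exists in one arm only. Sections 5.2 and 17.5 do not match 18.3 and 18.4, and 18.1 contradicts both 18.4 and the six-week examination in 5.1. Outcome 1 narrows the gap in intention but not in the data list or the analysis plan.

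The textual part rests on no assumption. The size of what is lost depends on event rates that the protocol does not give. At 50 per arm, a defined comparison would bound a zero count at 7.1%. It would detect a rise from an assumed 10% to 30% with about 64% power, but a rise from 10% to 20% with only about 19%. What is missing is thus a descriptive comparison of harm, not a test able to exclude it. It should still be corrected, because the trial looks to change standard care and the information is already charted.

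**What to change.** - **5.2 and 17.5:** list post-operative complications, for example reoperation, hardware exposure and surgical site infection, together with the Outcome 1 examination result. Take them up to the standard six-week visit from the charting in 18.3, for all randomised patients in both arms.
- **18.6:** replace the cross-reference with event counts by randomised arm and a risk difference with an exact 95% confidence interval, labelled as descriptive given 50 per arm.
- **10.2:** state that the repeat-procedure and hardware-exposure items apply at baseline only, so that such events after study surgery are counted as outcomes.
- **18.1:** reconcile with 18.4 and 5.1 on how long a patient is followed for study data.
- **18.7:** remove the statement that operating-room time cannot rise, since that is the hypothesis in 1.2.

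The cost is protocol wording and a few chart-derived REDCap fields from a visit that is already standard care. It needs no extra patients, visits or procedures.

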## TEMPLATE: RESEARCH PROTOCOL

NUMBER	ACTIVE DATE	PAGE
HRP-503	02-04-2020	23 of 35

### For patients:

A research team member will accompany a surgical team member to the pre-operative consultation appointment for a prospective study patient about to undergo treatment for a mandible fracture. The team member will bring the necessary consent forms.

During this appointment the surgeon will introduce the research team member first so they can introduce the study to determine patients' willingness to participate. That way if the patient isn't interested in participating minimum time out of the visit has been spent discussing study. If subject agrees, the study team member will begin the consenting process.

During the consenting process the research team member will go over all the details and timelines for the study. Contact information will also be provided so if any questions or concerns arise, they can contact the study team.

The study team will ensure that the patient is by no way obligated to participate in this study. The procedure and normal post operative standards of care will be provided if the patient participates or not. There will be adequate time for the patient to ask any question or discuss any concerns.

Participants will be provided a consent for both to review and take with them during their appointment visit. The one copy the research team will obtain the signature of the participant and the research team member that obtained the consent. This form will be kept in the regulatory binder in the research coordinators office in a locked filing cabinet in a personal office where only the study team members have access to.

